5.5.5.6 Immune-related Adrenal Insufficiency

Monitor for signs and symptoms of adrenal insufficiency. Evaluate adrenocorticotrophic hormone (ACTH) (a.m.), cortisol level (a.m.), and metabolic panel (sodium, potassium, carbon dioxide, and glucose). Consider ACTH stimulation test for indeterminate results. For evidence of primary adrenal insufficiency (high ACTH, low cortisol), evaluate for a precipitating cause of crisis, such as infection, and perform an adrenal computed tomography scan for metastasis/hemorrhage. For Grade 1 adrenal insufficiency, CX-072 may be held until subject is stabilized on replacement hormone. Withhold CX-072 for Grade 2, Grade 3, or Grade 4 events until the subject is stabilized on replacement hormones. Endocrinology should be consulted for all grades of adrenal insufficiency including for recommendations on replacement and stress dose steroid therapy.

5.5.5.7 Immune-related Type 1 Diabetes

Monitor subjects for hyperglycemia or other signs and symptoms of new or worsening diabetes mellitus, including measuring glucose at baseline. Laboratory evaluation in suspected Type 1 diabetes should include testing for ketosis in urine and an assessment of the anion gap on a metabolic panel. Withhold CX-072 for Grade 2, Grade 3, or Grade 4 events, perform urgent endocrine consultation for all subjects, and initiate insulin therapy for all subjects. Hold CX-072 until glucose control is obtained on therapy with reduction of toxicity to \leq Grade 1.

5.5.5.8 Immune-related Hypophysitis

Monitor for signs and symptoms of hypophysitis. Evaluate ACTH (a.m.), cortisol (a.m.), TSH, FT4, and electrolytes at baseline and determine whether hypophysitis or adrenal insufficiency is to be ruled out. Evaluate additional hormones (eg, follicle-stimulating hormone [FSH], luteinizing hormone [LH], testosterone, estrogen) as clinically indicated. Consider brain imaging (pituitary/sellar cuts) if clinically indicated. Consider holding CX-072 for Grade 1 events until subject is stabilized on replacement therapy. Withhold CX-072 for Grade 2, Grade 3, or Grade 4 events until the subject is stabilized on replacement hormones. Endocrinology should be consulted. Be aware of the need to start corticosteroids first when planning hormone replacement therapy for multiple deficiencies.

5.5.5.9 Immune-related Uveitis and Other Ocular Inflammatory Toxicities

Counsel subject to inform the Investigator of any vision changes, eyelid swelling, proptosis, or pain. Refer to ophthalmology for all subjects (within 1 week for all subjects for Grade 1 events; urgent referral for Grade >1 events). Withhold CX-072 for Grade 2 events until after ophthalmology consult. Treatment for Grade 1 uveitis includes artificial tears. Treatment for $>$ Grade 1 events includes topical and systemic corticosteroids. Resume CX-072 after return to \leq Grade 1. Permanently discontinue CX-072 for Grade 3 and Grade 4 uveitis or episcleritis. Blepharitis does not have a formal grading system. Treatment includes warm compresses and lubrication drops. CX-072 may continue unless the event is persistent and/or serious.

5.5.5.10 Immune-related Encephalitis or Meningoencephalitis

Monitor for changes in neurologic function. Withhold CX-072 for new onset or moderate to severe neurologic symptoms and evaluate to rule out infectious or other causes of neurologic deterioration. Withhold CX-072 for Grade 1, Grade 2, or Grade 3 events and consult with neurology. Consider concurrent IV acyclovir until polymerase chain reaction results are obtained and negative, and treatment with methylprednisolone and additional treatment (eg, IV immunoglobulin, rituximab as recommended by neurology consultation). Permanently discontinue CX-072 for confirmed diagnosis of autoimmune encephalopathy.

5.5.5.11 Immune-related Skin Toxicity

For rash and inflammatory dermatitis, Grade 1 toxicities should be treated with emollients and/or mild-moderate potency topical corticosteroids. Counsel subjects to avoid skin irritants and sun exposure. For Grade 2 toxicities, consider initiating prednisone (or equivalent) at 1 mg/kg, tapering over at least 4 weeks. In addition, treat with topical emollients, oral antihistamines, and topical medium to high potency corticosteroids. For Grade 3 toxicities, initiate 1 to 2 mg/kg (methyl)prednisolone (or equivalent), tapering over at least 4 weeks and treat also with topical emollients, oral antihistamines, and topical medium-high potency corticosteroids. Consult with dermatologist. For Grade 4 toxicities, treat with systemic corticosteroids IV (methyl)prednisolone (or equivalent) 1 to 2 mg/kg with slow tapering when the toxicity resolves. Admit subject immediately with urgent consult by dermatology.

For bullous dermatoses and severe cutaneous adverse reactions refer to Brahmer et al for additional guidance ([Brahmer 2018](#)). Refer to dermatology for blisters that are not explained by infectious/transient other causes (eg, herpes simplex, herpes zoster infections, pressure/friction bullae). When symptomatic bullae or erosions are observed on the skin or mucosal surfaces, the cutaneous irAE is, by definition, considered at least Grade 2.

5.5.5.12 Other Immune-related Adverse Reactions

For any suspected irAEs, exclude other causes. Based on the severity of the adverse reaction, withhold CX-072, administer high-dose corticosteroids, and/or if appropriate, initiate hormone replacement therapy. Upon improvement to Grade ≤ 1 , initiate corticosteroid taper and continue to taper over at least 1 month. Consider restarting CX-072 after completion of corticosteroid taper based on the severity of the event.

Refinement of the recommended treatment of TRAEs will be made as the study progresses.

If any of the immune-related symptoms worsen or do not improve with the guidelines above, tumor necrosis factor alpha (TNF α) inhibitors may be administered at the discretion of the Investigator.

5.5.6 Adverse Event Recovery Monitoring

If recovery of an AE is not seen within 4 weeks, the Investigator must review the subject with the Medical Monitor to determine if the subject should be permanently withdrawn from the study drug or a further period of waiting for resolution is warranted.

5.5.7 Treatment Compliance

CX-2009 and CX-072 will be administered only by study personnel by IV infusion at the study site. The infusion date and start and stop times will be recorded in the source documents and eCRF.

5.5.8 Storage and Accountability

It is the responsibility of the Investigator to ensure that the study drug is stored as specified by the Sponsor and in accordance with applicable regulatory requirements. Drug accountability details are provided in the Core ([Appendix A](#)).

CX-2009

CX-2009 vials must be stored at a temperature of 2°C to 8°C. Vials should be stored in the carton. Once CX-2009 has been prepared for administration, the total storage time (combination of refrigeration and room temperature) is not to exceed 24 hours. Stability data for CX-2009 supports 8 hours at room temperature/under room light and 24 hours at 2°C to 8°C in the refrigerator following dilution and transfer to the IV bag. Care must be taken to assure sterility of the prepared solution as the product does not contain any anti-microbial preservative or bacteriostatic agent. No incompatibilities between CX-2009 and polyolefin bags have been observed. Do not freeze.

CX-072

CX-072 vials must be stored upright at a temperature of 2°C to 8°C (36°F to 46°F). Vials should be stored in the carton. Once CX-072 has been prepared for administration, the total storage time (combination of refrigeration and room temperature) is not to exceed 24 hours. Stability data for CX-072 supports 8 hours at room temperature/under room light and 24 hours at 2°C to 8°C in the refrigerator following dilution and transfer to the IV bag. Care must be taken to assure sterility of the prepared solution as the product does not contain any anti-microbial preservative or bacteriostatic agent. No incompatibilities between CX-072 and polyolefin bags have been observed. Vials should be stored in the original carton until time of use. Do not freeze.

5.5.8.1 Product Complaints

A product complaint is any perceived deficiency related to physical, chemical or biological properties, or the labeling, or packaging of a product.

If the solution is cloudy, discolored, or contains extraneous particular matter, quarantine the product and report the deficiency on a Product Complaint Form as described in the Pharmacy Manual. A Complaint Investigator will follow-up to obtain additional information and provide instructions on how to return the product.

Record the product return on the Drug Accountability Log to ensure complete tracking of drug supply.

5.5.9 Discontinuation of CX-2009 for Adverse Events

Subjects with Grade 4 AEs requiring permanent discontinuation of CX-2009 as described in [Table 8](#) and [Table 9](#) must be discontinued. Subjects who fail to resolve AEs as described in

Section 5.5.6 must be discontinued unless a discussion between the Investigator and Medical Monitor documents that a further period of waiting for resolution is warranted.

Where CX-2009 and CX-072 are administered in combination (Parts D1, D2, E1, and E2), if, in the opinion of the Investigator, a toxicity is considered to be due solely to one component of the study treatment (ie, CX-2009 or CX-072) and the dose of that component is delayed, modified, or permanently discontinued in accordance with the guidelines in the Module, the other component may be administered if there is no contraindication.

5.5.10 Discontinuation of CX-072 for Adverse Events

Permanent discontinuation of CX-072 may be required as outlined in [Table 10](#).

Where CX-2009 and CX-072 are administered in combination (Parts D1, D2, E1, and E2), if in the opinion of the Investigator a toxicity is considered to be due solely to one component of the study treatment (ie, CX-2009 or CX-072), and the dose of that component is delayed, modified, or permanently discontinued in accordance with the guidelines in the Module, the other component may be administered if there is no contraindication.

CX-072 should be permanently discontinued for either of the following:

- Inability to reduce corticosteroid dose to ≤ 10 mg of prednisone or equivalent per day within 12 weeks of initiation of corticosteroid
- Persistent Grade 2 or 3 TRAEs that do not recover to Grade ≤ 1 or baseline or resolve within 12 weeks after the last dose of CX-072

For adverse reactions that do not recover within 4 weeks, the Investigator must contact the Sponsor Medical Monitor to determine if the subject should be permanently withdrawn from CX-072 or if a longer period of waiting for resolution is warranted.

5.5.11 Additional Guidelines

Refinement of the recommended management of TRAEs will be made as the study progresses.

5.6 Prior and Concomitant Medications and/or Procedures

5.6.1 Excluded Medications and/or Procedures

Medications taken within 30 days before the administration of study drug and concomitant medications and therapies administered during the study will be recorded on the relevant eCRF.

1. The use of herbal remedies, other marketed anticancer chemo/immunotherapy/hormonal drugs, or investigational drugs is not permitted.
2. New chemotherapy, hormonal, radiation, or immunotherapy are not permitted during the screening or treatment periods.

3. Palliative therapies (eg, focal radiotherapy for pain, thoracentesis or paracentesis for comfort) is permitted after consultation with the Medical Monitor. A subject whose brain metastases are progressing on head imaging and who requires radiotherapy will be withdrawn from the study drug.
4. The use of live vaccines is prohibited 28 days prior to the planned first dose of CX-2009, while on study drug, and for 90 days after the last dose of CX-2009. The use of any killed or attenuated vaccines for the prevention of influenza is permitted. The use of other killed or attenuated vaccines for the prevention of infectious diseases may be permitted on a case-by-case basis after discussion with the Medical Monitor. Any vaccinations administered during the study must be documented in the subject's medical records and in the eCRF.

Concomitant medications taken by the subject while in the treatment period should be recorded in the eCRF. After EOT, only concomitant medications administered for irAEs occurring within 90 days after last dose will be recorded. Once a subject enters the Follow-Up Period, only new therapies for the treatment of their cancer should be recorded in the eCRF.

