 13. Subjects who have received a live vaccine within 28 days prior to the planned first dose of CX-2009 (examples include, but are not limited to, the following: measles, mumps, rubella, chicken pox/zoster, yellow fever, rabies, Bacillus Calmette-Guérin, and typhoid vaccine);
 14. Participating in an ongoing clinical study involving treatment with medications, radiation, or surgery;

15. Women who are pregnant or breast feeding; or
16. Subjects who are >20.0% below their ideal body weight, as determined using the formula in [Appendix F](#).

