8.8 Module-Specified Events

Subjects with advanced cancer enrolling in this study who have received prior treatment may have some degree of bone marrow suppression from prior therapy and/or laboratory abnormalities due to underlying disease status. Only changes in the grade of baseline laboratory values that require intervention (eg, transfusions, delay in study drug administration) should be reported as AEs.

Common AEs observed with other maytansinoid or MTI (eg, auristatin) ADCs may be expected for CX-2009. These include:

- Blood and lymphatic system disorders: neutropenia, thrombocytopenia, and lymphopenia;
- Nervous system disorders: peripheral neuropathy (sensory and motor) and paresthesia;
- Eye disorders: blurred vision, dry eyes, and keratopathy (including corneal cyst, corneal disorder, corneal epithelial microcysts, keratitis, limbal stem cell deficiency, and punctate keratitis);
- General disorders and administration site conditions: fatigue, pyrexia, pain, confusion, and headache;
- Hepatotoxicity (including increases in AST or ALT);
- Hypokalemia;
- Hypomagnesemia;
- Pulmonary disorders: interstitial lung disease;
- Infections and infestations: upper respiratory tract infection;
- Gastrointestinal disorders: nausea, diarrhea, abdominal pain, vomiting, decreased appetite, and constipation;
- Skin and subcutaneous tissue disorders: rash and pruritus; and
- Respiratory, thoracic, and mediastinal disorders: cough and dyspnea.

Common AEs (>15%) observed with the use of CX-072 (10 mg/kg administered every 21 days; n=114) include:

- Fatigue (34%)
- Anemia (25%)
- Decreased appetite (23%)
- Diarrhea (22%)
- Nausea (22%)
- Increased AST (19%)
- Vomiting (18%)
- Cough (16%)
- Dyspnea (16%)

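### Section 5.6.1 item 4 bans live vaccines but then permits attenuated influenza vaccine, so the rule for a live attenuated influenza vaccine is inconsistent on treatment and for 90 days afterwards

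*Protocol*

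**What the plan says.** Protocol Section 5.6.1, item 4, has three sentences that matter here.

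- The first is a ban: "The use of live vaccines is prohibited 28 days prior to the planned first dose of CX-2009, while on study drug". It continues "while on study drug, and for 90 days after the last dose of CX-2009". It states no exception.
- The second is a permission: "The use of any killed or attenuated vaccines for the prevention of influenza is permitted". It has no time limit, no non-live qualifier and no consultation step.
- The third covers everything else: "The use of other killed or attenuated vaccines for the prevention of infectious diseases may be permitted on a case-by-case basis". That route requires discussion with the Medical Monitor.

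Item 4 then asks that any vaccination during the study be recorded in the medical record and the eCRF.

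The eligibility counterpart is exclusion 13 in Section 4.2, which excludes "Subjects who have received a live vaccine within 28 days prior to the planned first dose of CX-2009". Its list of examples is open ("examples include, but are not limited to, the following: measles, mumps, rubella" and others). It does not name influenza vaccine and makes no exception for it.

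**The concern.** In the permission, *attenuated* is set beside *killed* as the alternative to it, so it cannot mean killed. In ordinary vaccine usage it means a weakened live organism. A live attenuated influenza vaccine then meets both the ban and the permission, in consecutive sentences of one item.

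At stake is a conduct rule that sites apply directly. A site following the second sentence to the letter could give a live vaccine during treatment without consulting anyone. A monitor following the first sentence would record the same act as use of a prohibited medication.

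The documents give some reason to care about live vaccines in these subjects. Section 8.8 says "Common AEs observed with other maytansinoid or MTI (eg, auristatin) ADCs may be expected for CX-2009", and its list includes "Blood and lymphatic system disorders: neutropenia, thrombocytopenia, and lymphopenia".

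**Working it through.** The plan states no figure on this point, so the check is a comparison of texts. *Attenuated* is read in its ordinary sense.

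| Vaccine and timing | Item 4, sentence 1 | Item 4, sentence 2 | Item 4, sentence 3 | Exclusion 13 | Result |
|---|---|---|---|---|---|
| Killed influenza, on treatment | Silent | Permitted | Not applicable | Not applicable | Consistent |
| Live attenuated influenza, on treatment or within 90 days of last dose | Prohibited | Permitted, no consultation | Not applicable | Not applicable | Conflict |
| Other live attenuated vaccine, same period | Prohibited | Not applicable | Possible after Medical Monitor discussion | Not applicable | Same wording fault, but gated |
| Live attenuated influenza, 28 days before first dose | Prohibited | Permitted (no time limit stated) | Not applicable | Excluded | Exclusion 13 settles eligibility |

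The ungated conflict is therefore confined to one product class in one period: live attenuated influenza vaccine, during treatment and the 90 days after it.

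**Does other text resolve it?** Neither document defines *attenuated*. Core Section 9.7 (Prior and Concomitant Medications) leaves prohibited medications to the module and does not mention vaccines. The module's introduction says that it holds all guidelines needed to manage subject care safely, so item 4 is the operative rule.

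**Do other readings remove the fault?**
- If *attenuated* was meant as non-live, the ban stands alone and the rule is coherent, but the word is wrong.
- If the second sentence was meant as an exception for influenza, nothing links it to the ban, and exclusion 13 has no matching exception.

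Either way the text needs correcting.

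**How strong is the safety ground?**
- For: the class expectation in Section 8.8; the neutrophil decreases in monkeys in Section 1.3.2, largely reversed after a 21-day recovery period; and the hold rules for Grade 3 or 4 neutropenia in Section 5.5.4.1.
- Against: the clinical safety summary in Section 1.3.4.1, covering 92 subjects, names neither neutropenia nor lymphopenia, and none of the dose-limiting toxicities it lists is hematologic.

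**How many subjects?** SAP Section 4.2 gives those treated: 37 (Part A) + 39 (Part A2) + 10 (mTPI-2 cohort) + 3 (Part B) + 10 (Part C1) = 99. This is an upper bound. The documents do not say how many were treated under the present text of item 4, and they give no vaccination data.

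**The case against.** The best reply is that item 4, read as a whole, treats live vaccines as one class and killed or attenuated vaccines as another. On that view the drafter placed *attenuated* outside *live*, the ban covers every live influenza vaccine, and there is one poor word but no conflict. Alternatively, a specific permission following a general ban could be taken to prevail. Either approach yields a single answer.

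Part of this stands. The sponsor's intent is not known, and the inconsistency depends on a meaning that the documents neither supply nor displace. But the two approaches give opposite answers, and a site has no text by which to choose between them.

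It can also be said that an unqualified ban is accepted as decisive before dosing, so it should be decisive afterwards too. The difference is that exclusion 13 is a separate eligibility criterion with no competing permission beside it. After the first dose, only item 4 speaks.

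The practical objections carry more weight. Vaccinations must be recorded, so an event would be visible, although recording does not prevent it. SAP Section 1 reports that enrollment stopped on 07 July 2020. Section 1.3.4 gives a median exposure of 7.3 weeks (maximum 60) at 30 November 2019, so few subjects are likely to remain in the window.

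**Conclusion.** The point holds as a wording inconsistency in an operative safety rule, limited to live attenuated influenza vaccine on treatment and for 90 days after the last dose. It rests on the ordinary meaning of *attenuated*. The number of subjects affected cannot be stated and is probably small. It is worth correcting because the rule is meant to protect subjects and the correction is nearly free.

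A reader might infer more than the documents support:
- That the plan knowingly allows live vaccines on treatment. The intent cannot be established from the text.
- That subjects were harmed, or that 99 were exposed. No vaccination or related harm is reported, and 99 is only a ceiling on coverage.
- That eligibility is inconsistent as well. Exclusion 13 bars any live vaccine in the 28 days before dosing, and its open list reaches influenza vaccine without naming it.
- That other attenuated vaccines may be given freely. They need discussion with the Medical Monitor first.

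**What to change.** In the second and third sentences of item 4, replace *killed or attenuated* with *non-live (eg, inactivated, recombinant or subunit)*. Changing only *attenuated* to *inactivated* would be weaker: it nearly repeats *killed* and would not plainly cover recombinant or subunit vaccines.

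Add a clause to item 4 stating that live attenuated influenza vaccine falls under the prohibition in its first sentence. Optionally, add it to the examples in exclusion 13 so that the two sections match. The sponsor should confirm that this restrictive reading is the intended one.

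With enrollment closed, a written clarification to sites with subjects on drug or within 90 days of the last dose is sufficient. The corrected wording should carry into any later CX-2009 module. The cost is one phrase changed in two sentences, one added clause and, if wanted, one added example. Visits, data collection, sample size and analyses are unchanged.

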5.6.2 Restricted Medications and/or Procedures

Any other anticancer treatment such as chemotherapy, immunotherapy, biochemotherapy, radiotherapy, investigative therapy, or high-dose steroids (except to treat TEAEs) are prohibited during and within 30 days prior to receiving study drug. Luteinizing hormone-releasing hormone agonists are permitted for pre-menopausal women. For subjects with CRPC, overlapping anti-androgen therapy with CX-2009 is allowed. Anticoagulation therapy with warfarin is also prohibited.

Standard supportive medications may be used in accordance with institutional guidelines and Investigator discretion. These may include hematopoietic growth factors to treat neutropenia or thrombocytopenia in accordance with ASCO guidelines, transfusions, bone-targeted agents (bisphosphonates and/or RANK-L agents), antiemetics, antidiarrheals, and glucocorticoids, including treatment of an immune-related toxicity or short courses to treat asthma, chronic obstructive pulmonary disease, etc.

Continuation of standard of care medications (particularly hormonal related therapies for prostate carcinoma) that the subject has been on for the previous 30 days at stable doses are allowed.

See Section 5.7 for guidance on the avoidance of concomitant medications that are sensitive substrates of CYP3A or are CYP3A substrates with a narrow therapeutic index.

For Subjects Receiving CX-072 (Parts D1, D2, E1, and E2). Inhaled or intranasal corticosteroids (with minimal systemic absorption) may be continued if the subject is on a stable dose. Nonabsorbed intra-articular steroid injections will be permitted. Systemic corticosteroids required for the control of IRRs or irAEs must be tapered and must be at nonimmunosuppressive doses (<10 mg/day of prednisone or equivalent) prior to the next study drug administration. The

use of steroids as prophylactic treatment for subjects with allergies to diagnostic imaging contrast dyes will be permitted.

